9.2.1.4.2 Visit 4 (Day 34)

This is the second part of the two day visit. The final PK sample will be collected 24 hours after the Day 33 morning CLB dose.

Following completion of the PK sampling process the following observations will be made on Day 34: concomitant medications (including AEDs), physical examination (including body weight), vital signs and AEs.

At the end of the blinded phase of the study on Day 34, providing the investigator and patient both agree, patients will be invited to continue taking GWP42003-P and to enter the OLE.

Patients who enter the OLE will be dispensed GWP42003-P on Day 34 and the first dose will be taken in clinic. Following administration of GWP42003-P, patients must remain in clinic for at least 30 minutes to monitor for any adverse reactions. At the point of entry to the OLE, patients will be transitioned to the OLE treatment over a 10 day period in order to maintain blinding.

Patients who do not enter the OLE will begin a 10 day taper period during which they will taper off their daily dose of GWP42003-P/placebo. The daily dose will be reduced by 10% of the maintenance dose per day and treatment will end on Day 42.

9.2.1.5 Visit 5 (Patients not entering Open Label Extension) (Day 43 + 3 days)

This visit will occur 42 days after Visit 2, Day 1 (enrollment) for those patients who do not enter the OLE.

All GWP42003-P/placebo (used and unused) will be collected and a check of the returned GWP42003-P/placebo against usage must be made. A physical examination (including body weight), ECG and vital signs will be assessed and the C-SSRS will be administered. The trained investigator or study coordinator will complete the Study Medication Use and Behavior Survey as an interview with the patient/caregiver. Clinical laboratory samples (blood and urine) will be taken for hematology, biochemistry and urinalysis and a review of concomitant medications (including AEDs) and AEs will be completed. Patient diaries will be collected.

9.2.1.6 Visit 6 - Safety Follow up Call (Day 71) (\pm 3 days)

This visit is required for patients who do not enter the OLE study on Day 34, or who withdraw from the study early. This visit should occur four weeks after Visit 5, (\pm 3 days) or withdrawal from treatment, and can be conducted over the telephone. The following observations will be made on Day 71: concomitant medications (including AEDs) and AEs.

9.2.2 Open Label Extension

Patients who enter the OLE will be dispensed IMP at Visit 4 (Day 34) and will have regular clinic visits for a maximum of one year or earlier (if marketing authorization is granted or the patient withdraws). The visit schedule is calculated relative to Visit 4 (Day 34).

9.2.2.1 Visit 5 (Open Label Extension) - Two Weeks (\pm 3 days)

This visit will occur two weeks after Visit 4 (Day 34). Patients will return all used and unused IMP. The following observations will be made at Visit 5 (OLE): concomitant medications (including AEDs), physical examination (including body weight), ECG, vital signs, review of seizure diary and AEs.

Clinical laboratory samples (blood and urine) will be taken for hematology, biochemistry and urinalysis. The C-SSRS will be administered. The investigator must record the patient's attendance at the visit and the outcome.

The investigator must assess adherence to the dosing regimen and recording of rescue medications by reviewing the patient's diary.

The GWP42003-P dose may be adjusted up or down by the investigator from the maintenance dose of 20 mg/kg/day achieved at the end of the 10-day transition period, up to a maximum of 30 mg/kg/day in the OLE period.

9.2.2.2 Visit 6 (Open Label Extension) - One Month (\pm 3 days)

This visit will occur one month (one month is considered as 28 days) after Visit 4 (Day 34). Patients will return all used and unused IMP. The following observations will be made at Visit 6 (OLE): concomitant medications (including AEDs), physical examination (including body weight), ECG, vital signs, review of seizure diary and AEs.

Clinical laboratory samples (blood and urine) will be taken for hematology, biochemistry and urinalysis. The C-SSRS will be administered. The investigator must record the patient's attendance at the visit and the outcome.

The investigator must assess adherence to the dosing regimen and recording of rescue medications by reviewing the patient's diary.

9.2.2.3 Visit 7 (Open Label Extension) - Two Months (\pm 3 days)

This visit will occur two months after Visit 4 (Day 34). Patients will return all used and unused IMP. The following observations will be made at Visit 7 (OLE): concomitant medications (including AEDs), physical examination (including body weight), ECG, vital signs, review of seizure diary and AEs.

Clinical laboratory samples (blood and urine) will be taken for hematology, biochemistry and urinalysis. The C-SSRS will be administered. The investigator must record the patient's attendance at the visit and the outcome.

The investigator must assess adherence to the dosing regimen and recording of rescue medications by reviewing the patient's diary.

9.2.2.4 Visit 8 (Open Label Extension) - Three Months (\pm 7 days)

This visit will occur three months after Visit 4 (Day 34). Patients will return all used and unused IMP. The following observations will be made at Visit 8 (OLE): concomitant medications (including AEDs), physical examination (including body weight), ECG, vital signs, review of seizure diary and AEs.

Clinical laboratory samples (blood and urine) will be taken for hematology, biochemistry and urinalysis. The C-SSRS will be administered. The investigator must record the patient's attendance at the visit and the outcome.

The investigator must assess adherence to the dosing regimen and recording of rescue medications by reviewing the patient's diary.

9.2.2.5 Visit 9 (Open Label Extension) - Six Months (\pm 7 days)

This visit will occur six months after Visit 4 (Day 34). Patients will return all used and unused IMP. The following observations will be made at Visit 9 (OLE): concomitant medications (including AEDs), physical examination (including body weight), ECG, vital signs, review of seizure diary and AEs.

Clinical laboratory samples (blood and urine) will be taken for hematology, biochemistry and urinalysis. The C-SSRS will be administered. The investigator must record the patient's attendance at the visit and the outcome.

The investigator must assess adherence to the dosing regimen and recording of rescue medications by reviewing the patient's diary.

9.2.2.6 Visit 10 (Open Label Extension) - Nine Months (\pm 7 days)

This visit will occur nine months after Visit 4 (Day 34). Patients will return all used and unused IMP. The following observations will be made at Visit 10 (OLE): concomitant medications (including AEDs), physical examination (including body weight), ECG, vital signs, review of seizure diary and AEs.

Clinical laboratory samples (blood and urine) will be taken for hematology, biochemistry and urinalysis. The C-SSRS will be administered. The investigator must record the patient's attendance at the visit and the outcome.

The investigator must assess adherence to the dosing regimen and recording of rescue medications by reviewing the patient's diary.

9.2.2.7 Visit 11 (Open Label Extension End of Treatment) - Twelve Months (\pm 7 days)

This visit will occur twelve months after Visit 4 (Day 34). Patients will return all used and unused IMP. The following observations will be made at Visit 11 (OLE): concomitant medications (including AEDs), physical examination (including body weight), ECG, vital signs, review of seizure diary and AEs.

Clinical laboratory samples (blood and urine) will be taken for hematology, biochemistry and urinalysis. The C-SSRS will be administered. The investigator must record the patient's attendance at the visit and the outcome.

The investigator must assess adherence to the dosing regimen and recording of rescue medications by reviewing the patient's diary.

Starting at Visit 11, patients will begin to taper down their IMP dose. The dose will be reduced by 10% of their OLE maintenance dose per day.

9.2.2.8 Visit 12 (Open Label Extension End of Taper)

This visit will be ten days after Visit 11. All IMP (used and unused) will be collected and a check of the returned IMP against usage must be made. A physical examination (including body weight), ECG and vital signs will be assessed and the C-SSRS will be administered. The trained investigator or study coordinator will complete the Study Medication Use and Behavior Survey as an interview with the patient/caregiver.

Clinical laboratory samples (blood and urine) will be taken for hematology, biochemistry and urinalysis and a review of concomitant medications (including AEDs) and AEs will be completed. Patient diaries will be collected and reviewed.

9.2.2.9 Safety Follow Up Call (\pm 3 days)

This visit will occur one month after the OLE End of Taper and can be conducted over the telephone. The following observations will be made during the follow up call: concomitant medications (including AEDs) and AEs.

10. WITHDRAWAL

In accordance with the Declaration of Helsinki³¹, the FDA regulations relating to good clinical practice (GCP) and clinical trials^{32,33,34}, the EU Clinical Trials Directive (2001/20/EC)³⁵ and/or other applicable regulations, a patient has the right to withdraw from the study at any time and for any reason without prejudice to his or her future medical care by the physician or at the institution.

The patient must be withdrawn from the study if any of the following apply:

- Administrative decision by the investigator, GW, or a Regulatory Authority.
- Pregnancy.
- Protocol deviation that is considered to potentially compromise the safety of the patient.
- Withdrawal of patient consent.
- Withdrawal of legal representative consent.
- Lost to follow up.
- ALT $> 3 \times$ ULN or AST $> 3 \times$ ULN **and** (TBL $> 2 \times$ ULN **or** INR > 1.5).
- ALT or AST $> 3 \times$ ULN with the appearance of fatigue, nausea, vomiting, right upper quadrant pain or tenderness, fever, rash, and/or eosinophilia ($> 5\%$).
- ALT or AST $> 8 \times$ ULN.
- ALT or AST $> 5 \times$ ULN for more than two weeks.
- Any other IMP is taken as part of a clinical trial during the study.

- Significant change in QTcB (> 60 msec) from the previous ECG or absolute QTcB of > 500 msec.

Patients may also be withdrawn from the study for any of the following:

- Patient non-compliance.
- AE, which in the opinion of the investigator, would compromise the continued safe participation of the patient in the study.
- Any evidence of drug abuse or diversion.
- Suicidal ideation or behavior of type four or five during the treatment period, as evaluated with the C-SSRS.

Should a patient request or decide to withdraw from the study, all efforts must be made to complete and report the observations as thoroughly as possible up to the date of withdrawal. Patients who withdraw should have their dose of IMP tapered gradually (10% each day) over a period of 10 days, beginning at the time the decision is made to discontinue. In some cases, tapering the dose of IMP may be inadvisable (e.g., continued dosing is not possible due to an AE). The decision on whether or not to taper IMP will be left to the investigator's clinical judgment. All assessments required at Visit 4 (if the withdrawal is during the blinded phase) or Visit 11 (if the withdrawal is during the OLE) should be conducted if possible. If the tapered dose is administered, patients should return for Visit 5 (if withdrawal is during the blinded phase) or Visit 12 (if the withdrawal is during the OLE) if possible. Wherever possible, the safety follow-up visit should be conducted 28 days from the date of the last dose of IMP. Patients withdrawing due to an AE should be followed up according to [Section 12.7](#). All information should be reported on the applicable CRF pages

11. URGENT SAFETY MEASURES

The sponsor and investigator may take appropriate urgent safety measures in order to protect the patients of a clinical trial against any immediate hazard to their health or safety. If such measures are taken by the investigator they must notify GW immediately or at least within 24 hours of awareness. GW will report urgent safety measures to Competent Authorities by telephone within 24 hours of awareness, wherever possible, and will provide a written report to the Competent Authorities and IRB/EC within three days.

12. ADVERSE EVENT REPORTING

12.1 Definitions

12.1.1 Adverse Event

For the purposes of this study an AE is defined as:

Any new unfavorable/unintended signs/symptoms (including abnormal laboratory findings), or diagnosis or worsening of a pre-existing condition, which is present following screening (Visit 1) throughout the study and up to the post treatment, safety follow-up visit (28 days after last dose of IMP), which may or may not be considered to be related to the IMP. Any event that is the result of a study procedure must be recorded as an AE.

Surgical/Investigational procedures are not AEs. The medical reason for the procedure is the AE. Elective hospitalizations for pre-study existing conditions or elective procedures are not AEs. The exception may be if the patient has an AE during hospitalization which prolongs their scheduled hospital stay in which case it would be considered a SAE (refer to [Section 12.2](#)).

If reporting a fatal event, the SAE term should be the underlying cause of the death (e.g., disease or medical condition leading to death).

12.1.2 Investigator

The term 'investigator' refers to the study PI or a formally delegated study physician.

12.2 Serious Adverse Events

During clinical investigations, AEs may occur which, if suspected to be IMP related, might be significant enough to lead to important changes in the way the IMP is developed (e.g., change in dose, population, monitoring need, consent forms). This is particularly true for events that threaten life or function. Such SAEs will be reported promptly to Regulatory/Competent Authorities, applicable IRB/ECs and Investigators (expedited reporting) by GW.

An AE must only be classed as serious i.e., an SAE, when the event falls into one of the following criteria:

- Results in death.
- Is life-threatening.*
- Requires inpatient hospitalization or prolongation of existing hospitalization.
- Results in persistent or significant disability/incapacity.

- Is a congenital anomaly/birth defect.
- Medically significant.^{**}

* The term “life-threatening” in the definition of “serious” refers to an event in which the patient was at risk of death at the time of the event; it does not refer to an event, which hypothetically might have caused death if it were more severe.

** Medical and scientific judgment should be exercised in deciding whether SAE reporting is appropriate in other situations. Important medical events may not be immediately life threatening or result in death or hospitalization but may jeopardize the patient or may require intervention to prevent one of the other outcomes listed in the definition above. These should also usually be considered serious. Examples of such events are intensive treatment in an emergency room or at home for allergic bronchospasm; blood dyscrasias or convulsions that do not result in hospitalization; or development of drug dependency or drug abuse.

12.3 Reporting Procedures for Serious Adverse Events

All SAEs occurring during the study must be reported to GW with any other supporting information and recorded in the AE section of the CRF. Any on-going SAEs should be followed up until resolution wherever possible. For all deaths, the working diagnosis or cause of death as stated on a death certificate, available autopsy reports and relevant medical reports should be sent to GW promptly.

All SAEs must be reported directly to GW PVD within 24 hours of discovery or notification of the event. All SAE information must be recorded on the SAE forms provided in the site files and faxed to GW PVD. Additional information received for a case (follow-up or corrections to the original case) need to be detailed on a new SAE form, signed/dated and faxed to the GW PVD and the AE section of the CRF must be updated.

The investigator should continue to document all AEs which occur up to the last formal follow-up visit (Visit 13 for patients entering the OLE and Visit 6 for those patients that are not entering the OLE). If the investigator subsequently becomes aware of any deaths or a new IMP-related SAE after the last formal follow-up period of the study, these should still be reported to the GW PVD.

Any other problem discovered outside these time limits which is deemed to be an unexpected safety issue and is likely to have an impact on patients who have participated in the study, then these should be treated as an SAE and reported to GW PVD. Such post study SAEs do not need to be recorded on the patient’s CRF if editing rights to the CRF have been removed.

Contact details for the GW PVD are provided at the front of the site files for all study centers, and upon the GW SAE Report form.

12.4 Pregnancy

Any patient, or patient's partner, who has become pregnant whilst receiving IMP, or within 90 days of last dose of IMP, must be reported to the GW PVD within 24 hours of first awareness. Please use the GW Pregnancy Monitoring Forms provided. Where possible the investigator should provide the outcome of the pregnancy.

The investigator is not obliged to actively monitor for any pregnancies that commence more than 90 days after the final dose of IMP. However, if the investigator becomes aware of a new pregnancy outside this time limit then they should report it as above. GW PVD will follow up for all pregnancy outcomes.

12.5 Causality Assessment

Causality assessment is required for all AEs and SAEs. Causality assessment must only be assigned by the investigator. All cases judged as having a reasonable suspected causal relationship to the study medication must be reported as such. The expression "*reasonable causal relationship*" is meant to convey in general that there are facts (evidence) or arguments to suggest a causal relationship.

The following question which must be answered by the investigator for all AEs is used to capture the reasonable causal relationship of an event to the study medication:

"In your opinion is there a plausible relationship to the study medication?" The answer is "yes" or "no".

Events that start before the first dose of study medication (pre-treatment) should be considered as not causally related. Where a pre-treatment event worsens in severity following the first dose of study medication, a new event record should be entered into the CRF.

Considering the explanation given above, investigators are strongly encouraged to express their opinion on what the cause of an AE might be. For individual patients, the investigator is usually in the best position to assess the underlying suspected cause of an AE. For all AEs and especially SAEs, it is important that the investigator assess not only the possible role of the study medication but also competing etiological factors as the underlying cause. Factors for consideration may include:

- Medical history.
- Lack of efficacy/worsening of treated condition.
- Concomitant or previous treatment.

- Withdrawal of study medication.
- Protocol-related procedure.

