When describing the severity of an AE the terms mild, moderate, or severe should be used. Clinical judgment should be used when determining which severity applies to any AE.

If the severity of an AE fluctuates day-to-day, for example, a headache or constipation, the change in severity should not be recorded each time, instead only the worst observed severity should be recorded with AE start and stop dates relating to the overall event duration regardless of severity.

A severe AE is not the same as a SAE. For example, a patient may have severe vomiting but the event does not result in any of the SAE criteria above. Therefore it should not be classed as serious.

E) Causality

See [Section 12.5](#) above.

F) Action Taken with Study Medication

This question refers to the action taken with the IMP due to an AE. The action with the IMP must be classed as:

- None.
- Dose reduced temporarily.
- Dose reduced.
- Study medication interrupted.
- Study medication stopped.

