13.6.4.2 Adverse Events

AEs will be coded according to the Medical Dictionary for Regulatory Activities dictionary.

A treatment emergent AE is one that started, or worsened in severity or seriousness, following the first dose of IMP.

Descriptive presentations of treatment emergent AEs will be given by preferred term and system organ class for the safety analysis set. The number of patients reporting at least one AE will be provided. Summaries will be provided for each phase of the study separately.

The following summaries will be produced:

- All-causality AEs.
- Treatment related AEs.
- All-causality AEs by severity.
- All-causality serious AEs.
- Treatment related serious AEs.
- AEs reported as leading to permanent cessation of study treatment.
- Fatal AEs.

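### Section 12.5 asks for no new record when a pre-treatment event becomes serious at unchanged severity, though 13.6.4.2 counts it as treatment emergent, and it directs an unrelated causality answer

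*Protocol*

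**What the plan says.** Two sentences of protocol section 12.5 govern an event that began before dosing. One sets causality: "Events that start before the first dose of study medication (pre-treatment) should be considered as not causally related". The next sets the recording rule: "Where a pre-treatment event worsens in severity following the first dose of study medication, a new event record should be entered".

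Section 13.6.4.2 defines the analysis category: "A treatment emergent AE is one that started, or worsened in severity or seriousness, following the first dose of IMP". Among the tables it lists is "Treatment related serious AEs".

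Section 12.6, item D, grades severity as mild, moderate or severe and keeps it apart from seriousness: "A severe AE is not the same as a SAE". Section 12.2 defines seriousness by outcome, hospitalization being one example.

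Two further provisions bear on the point. Section 12.5 also states "Causality assessment is required for all AEs and SAEs". Section 12.3 states "All SAEs must be reported directly to GW PVD within 24 hours of discovery or notification of the event", and requires the AE section of the CRF to be updated when further information arrives.

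**The concern.** The instruction to sites is narrower than the definition used in the analysis. Because the protocol treats severity and seriousness as different attributes, the severity trigger in 12.5 cannot be read as covering an event that becomes serious without a change of grade. For such an event, a site following 12.5 leaves one record with a pre-dose start date and answers no to the causality question.

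The preset answer matters more than the missing line. A flag can sometimes be rebuilt from other data. A causality opinion that the site was told not to give cannot be rebuilt at analysis, and 12.5 reserves causality assessment to the investigator. Safety and tolerability of GWP42003-P in the presence of clobazam is the secondary objective. With 20 patients, a single serious event is visible in the tables.

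**Working it through.** The protocol gives no figure to reproduce. The check sets the two rules side by side for an AE that starts after screening and before the first dose.

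| What happens after first dose | Record and causality under 12.5 | Status under 13.6.4.2 | Agree? |
|---|---|---|---|
| Severity grade worsens | New record, causality assessed on that record | Treatment emergent | Yes |
| Nothing changes | No new record, unrelated by default | Not treatment emergent | Yes |
| Grade unchanged, event becomes serious | No new record required, pre-dose start date stands, unrelated by default | Treatment emergent | No |

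Only the third row fails.

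Next, does another section close the gap?

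- **12.6, items A to F.** The items required for every AE are event, dates, outcome, severity, causality and action taken. Neither seriousness nor the date an event became serious is among them. Item E refers back to 12.5.
- **12.3.** The SAE goes to pharmacovigilance on an SAE form and the CRF AE section is updated. No new event record is required, and nothing lifts the default in 12.5.
- **12.1.1.** Worsening of a pre-existing condition counts as an AE, so a worsened medical-history condition can be entered as a new event. There is no rule for splitting an AE already recorded before dosing that later becomes serious.
- **12.5 itself.** It asks for causality on every AE and SAE, but directs the answer for those that began before dosing.

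So the gap mainly concerns AEs with onset between screening and first dose. Visit 2 Day 1 falls 7 to 14 days after Visit 1 and dosing starts a day later, which gives 7 + 1 = 8 to 14 + 1 = 15 days, or 15 + 3 = 18 with the visit window.

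For the weight of one event: at 4:1 in 20 patients the arms are 20 × 4/5 = 16 and 20 × 1/5 = 4, so one patient is 1/16 = 6% of the active arm or 1/4 = 25% of the placebo arm. These figures describe arm size and do not say how often the case will occur.

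**The case against.** The strongest reply is that 12.5 sets no analysis category. Treatment-emergent status comes from 13.6.4.2, and an event that became serious on drug meets that definition however many CRF lines it has. This stands. A reader might infer that such an event stays pre-treatment and is absent from the treatment-emergent tables. The documents do not support that; they show only that the AE record 12.5 calls for does not reveal the event's status.

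A reader might also infer that the seriousness part of the definition cannot be met from the data collected, or that the SAE escapes safety review. Neither follows. Under 12.3 the event is reported within 24 hours on a dated form and the CRF is updated. Section 12.7 recognises relatedness as judged by the investigator or the sponsor, so the site's answer is not the only route to follow-up.

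It is also fair that 12.5 does not say a new record is forbidden in other cases, that its default is worded as a should, and that the same section urges investigators to weigh the role of study medication, above all for SAEs. These points soften the rule but leave the section giving two directions at once, and no other section supplies a trigger for seriousness.

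Finally, the case is narrow. Exclusion 6.2.6 keeps out patients with clinically relevant symptoms or significant illness, other than epilepsy, in the four weeks before screening or enrollment. Worsening seizures must be recorded as AEs, and hospitalizations due to epilepsy go through the SAE process. An event that newly needs admission would often be regraded, which triggers 12.5 as written. All of this lowers the frequency. None of it reconciles the two rules.

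**Conclusion.** The mismatch is in the current text and the rule is wrong as written, with minor impact. For a pre-treatment AE that becomes serious on study drug at the same grade, 12.5 leads the site to a record that cannot be relied on to show treatment emergence. Its causality default keeps the event out of the table of treatment-related serious events even if the event is correctly flagged as treatment emergent.

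The number of such events cannot be derived from the documents. The pre-dose share of observation to Day 33 can be computed, from 8/(8 + 32) = 20% to 18/(18 + 32) = 36% with 32 blinded dosing days (Days 2 to 33). That is a share of calendar days and not a probability of the event. It also leaves out the taper, the extension and follow-up, so it should not be used as a measure of size. The primary pharmacokinetic objective is untouched and safety is summarized descriptively.

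The conclusion assumes that sites follow the two sentences of 12.5 as written and that no instruction outside the protocol, such as a CRF completion guideline, already adds the missing trigger.

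**What to change.** Change two things in section 12.5:

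1. Require a new event record, with its own start date and its own causality assessment, where a pre-treatment event worsens in severity or becomes serious after the first dose.
2. Limit the unrelated default to pre-treatment events that worsen in neither respect after the first dose.

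This brings 12.5 into line with 13.6.4.2, which needs no change. Carry the same wording into the CRF completion guideline. The cost is a few words and an occasional extra AE record; no dose, visit or procedure is affected.
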